#### 4.8.1.1. Adverse Events and Serious Adverse Events

Adverse events (including serious adverse events (SAE), AEs causing permanent treatment discontinuation, deaths, and AEs of special interest) are recorded from the time of signed informed consent until the end of study. All AEs diagnosed by the Investigator will be reported and described.

All AEs will be dictionary coded by "lowest level term (LLT)", "preferred term (PT)", "high level term (HLT)", "high level group term (HLGT)" and associated primary "system organ class (SOC)" using the latest version of MedDRA at the time of the first database lock.

#### Adverse Event Observation Period

• Pre-treatment AEs are AEs that developed or worsened or became serious during the pre-treatment period.

Regeneron Pharmaceuticals, Inc.

Page 25 of 88

Protocol: R4461-PLD-20100

• TEAEs are AEs that developed or worsened or became serious during the respective TEAE period.

Protocol: R4461-PLD-20100

Date: May 16, 2024

• Post-treatment AEs are AEs that developed or worsened or became serious during the post-treatment period.

# 4.8.1.2. Adverse Events of Special Interest

Adverse events of special interest (AESI) are AEs (serious or non-serious) required to be monitored, documented, and managed in a pre-specified manner. AESIs will be recorded on the adverse event e-CRF using dedicated tick boxes, and/or identified using standard MedDRA queries (SMQ), company MedDRA queries (CMQ), MedDRA terms, and/or applicable laboratory assessments. Appendix 10.3 contains the definitions used to identify AESIs:

#### The AESIs include:

- Hypoglycemia, defined as blood glucose <54 mg/dL (eCRF, lab data)
- New onset diabetes mellitus (NODM) (eCRF, lab data)
- For patients with no diabetes at baseline, NODM is defined using the following lab parameters:
  - a. Two values of fasting ( $\geq 8$  hours) plasma glucose  $\geq 126$  mg/dL (7.0 mmol) during the treatment period

OR

- b. Two values of HbA1c ≥6.5% (48 mmol/mol) during the treatment period
- Hyperglycemia requiring treatment (eCRF, lab data), defined using the following lab parameter:
  - a. HbA1c ≥10.5% AND at the same visit an increase in HbA1c of ≥1.5% from baseline value

OR

- b. Fasting glucose ≥250 mg/dL on 2 occasions including symptoms consistent with hyperglycemia AND increase in fasting glucose >50 mg/dL above baseline
- Development of new or worsening of autoimmune disease (eCRF)
- Moderate or severe hypersensitivity reactions (CMQ, eCRF)
- Moderate or severe infusion reactions (eCRF)

## 4.8.1.3. Adverse Events of Interest

Adverse events of interest are AE's for which additional documentation is collected. Adverse events of interest include:

- Injection site reaction, collected from the eCRF
- Mild infusion reaction collected from the eCRF
- Mild hypersensitivity reactions from the eCRF

Regeneron Pharmaceuticals, Inc.

Page 26 of 88

# 4.8.1.4. Events Causing Death

The observation periods for patient deaths are per the observation periods defined above.

- Death on-treatment: deaths occurring during the respective TEAE period.
- Death post-treatment: deaths occurring during the post-treatment period.

# 4.8.2. Laboratory Safety Variables

Clinical laboratory tests will consist of blood analyses (including hematology, clinical chemistry and other) and urinalysis. Clinical laboratory values will be converted and analyzed in international units and US conventional units, with associated normal ranges provided by the central laboratory. Both actual test values and "change from baseline" values (defined as the post-baseline value minus the baseline value) will be used in the result summaries. Potentially clinically significant values (PCSV) ranges will be applied to the laboratory test values as applicable (see Appendix 10.4 for PCSV definitions). For those laboratory tests that do not have PCSV ranges, central laboratory normal ranges will be applied to identify out-of-range values. All laboratory samples will be collected before study treatment administration during the protocol scheduled visits, unless otherwise indicated.

Unless otherwise specified below, blood samples for clinical laboratories will be collected at the protocol scheduled visits, and visits will be assigned to the Global Analysis Windows (See Appendix 10.2). The laboratory parameters (excluding those considered as efficacy parameters) will be classified as follows:

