# 4.7. Efficacy Variables

Efficacy will be assessed through the following parameters: fasting TG, HbA1c, fasting glucose, liver fat content as measured by MRI-PDFF, and lipodystrophy hunger questionnaire outcomes.

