## Other

• Fasting Leptin, Pregnancy test (serum/urine), Fasting Free Fatty Acids, Hepatitis B surface antigen (sAg), HIV (Ab), HbA1c, Fasting Apolipoprotein C3, Fructosamine, Hepatitis C (Ab), Fasting ANGPTL3, Urine albumin and creatinine

Protocol: R4461-PLD-20100

Date: May 16, 2024

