### **10.2.** Windows for Analysis Time Points

Below are the definitions for the visit windows programmatically imposed on measures repeatedly collected over the course of the study. These visit windows reflect the study schedule of assessments as described in the protocol.

The visit windows are constructed using ranges applied to the number of days in study (study days) when the measure is collected. Below are the relevant definitions for the analysis visit windows:

1. Study day is defined as the number of days since the first study treatment administration +1. The first study treatment occurs on Day 1.

Protocol: R4461-PLD-20100

2. Single-blind study day is defined as the number of days since the first single-blind study treatment administration+1. Especially, Single-blind Study Day 1 (SB Day 1) is defined as the day for the first single-blind study treatment administration.

Protocol: R4461-PLD-20100

- 3. Since the protocol specifies that measurements be collected before study treatment is administered on a given day, it is appropriate that baseline include Day 1.
- 4. For randomized but not treated patients, Day 1 is the day of randomization.

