**Table 8: General Global Analysis Windows** 

Visit Label	Targeted DBTP Study Day	Targeted SBTP Study Day	Analysis Window in DBTP Study Days	Analysis Window in SBTP Study Days	
Screening	< Day -28	N/A	Measurement obtained prior to 1st study trt, and not defined as baseline visit	N/A	
Baseline	Day 1	N/A	Measurement obtained closest to 1st study trt, while remaining prior to 1st study trt.admin	N/A	
Week 1	8	N/A	Day 2 to Day 15	N/A	
Week 3	22	N/A	16 to 32	N/A	
Week 6	43	N/A	33 to 50	N/A	
Week 8	57	N/A	51 to 64	N/A	
Week 10	71	N/A	65 to 78	N/A	
Week 12	85	N/A	79 to SB Day 1	N/A	
Week 13	N/A	SB Day 8	N/A	SB Day 2 to 15	
Week 15	N/A	22	N/A	16 to 29	
Week 17	N/A	36	N/A	30 to 39	
Week 18	N/A	43	N/A	40 to 50	
Week 20	N/A	57	N/A	51 to 64	
Week 22	N/A	71	N/A	65 to 78	
Week 24	N/A	85	N/A	79 to 92	
FU- W5	Last study trt admin day + 35 days	Last study trt admin day +15 days TO last study trt admin day + 49 days			
FU-W9	Last study trt admin day + 63 days	Last study trt admin day + 50 days TO last study trt admin day + 77 days			
FU-W13	Last study trt admin day + 91 days	Last study trt admin day + 78 days TO last study trt admin day + 105 days			
FU-W17	Last study trt admin day + 119 days	Last study trt adı	min day + 106 days TO la 126 days	st study trt admin day +	

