Study Period			Dou	ble Bl	ind T	reatm	ent Per	riod (	TP1)	)				S	Single	e Blii	nd Ti	reatn	nent I	Perio	od (T	P2)			E O T / E T 12	Fo	ff-[name] llow Perio	y up	E O S
	In - Cli nic O ut pa tie nt vis it		In-	-Clinio	: Outp	atient	visit o	r Re	mote	visi	t		I n-Cl ini c O ut pa tie nt vis it		In-C	linic	Outj	patie	nt vis	it or	Ren	ıote	visit		O		-Clin	ic t visi	t
Visit Number:	œ	6	10	11	12	13	14	15	16	17	18	19	20	21	22	23	24	25	26	27	28	29	30	31	32	33	34	35	36
Day:	1	8	15	22	29	36	43	50	57	64	71	78	85	92	66	106	113	120	127	134	141	148	155	162	169	197	225	253	281
±visit window (d):		±3	±3	±3	±3	±3	±3	± 3	± 3	± 3	± 3	± 3	± 3	± 3	± 3	± 3	± 3	± 3	±3	± 3	± 3	± 3	± 3	± 3	± 3	± 7	± 7	± 7	± 7
Week:		1	2	3	4	5	9	7	8	6	10	11	12	13	14	15	16	17	18	19	20	21	22	23	24	28	32	36	40
Fasting Triglycerides 	X		X		X		X		X		X	X	X		X		X		X		X		X	X	X	X	X	X	X
Lipid Panel 	X						X						X						X				X		X	X	X	X	X
Fasting Glucose 	X		X		X		X		X		X	X	X		X		X		X		X		X	X	X	X	X	X	Χ
HbA1c	X				X		X				X		X				X		X				X		X	X	X	X	X
Fructosamine	X		X		X		X		X		X		X		X		X		X		X		X		X	X	X	X	X
Insulin 	X		X		X		X				X		X				X		X				X		X	X	X	X	X
Free Fatty Acids 	X		X		X		X				X		X				X		X				X		X	X	X	X	X
NMR Lipid panel LDL-C, HDL-C, total- Cholesterol 	X												X												X				X
Urine Creatinine and Albumin	X						X						X						X						X				X

Regeneron Pharmac Statistical Analysis			nc.																		P	roto	ocol				LD-2 y 16		
Study Period			Dou	ible Bl	ind T	reatm	ent Per	riod (	TP1)	)				S	Single	e Blir	nd Ti	reatn	nent I	Perio	d (T	P2)			E O T / E T 12	Fo	ff-Dru Safety Illow u Period	y up	E O S
	In - Cli nic O ut pa tie nt vis		In-	-Clinio	c Outp	oatient	t visit o	r Rei	mote	· visit	t		I n- Cl ini c O ut pa tie nt vis it		In-C	linic	Outp	oatie	nt visi	it or	Rem	iote :	visit		o		-Clini ttient		
Visit Number:	8	6	10	11	12	13	14	15	16	17	18	19	20	21	22	23	24	25	26	27	28	29	30	31	32	33	34	35	36
Day:	1	8	15	22	29	36	43	50	57	64	71	78	85	92	99	106	113	120	127	134	141	148	155	162	169	197	225	253	281
±visit window (d):		±3	±3	±3	±3	±3	±3	± 3	± 3	± 3	± 3	± 3	± 3	± 3	± 3	± 3	± 3	± 3	±3	± 3	± 3	± 3	± 3	± 3	± 3	± 7	± 7		± 7
Week:		1	2											23	24	28	32	36	40										
Daily Lipodystrophy Hunger questionnaire	-			-				'					— у	ζ —							•	•				•			→
BPI-SF questionnaire	X												X												X				X
SF-36 questionnaire	X												X												X				X

PHQ-8 questionnaire

HADS questionnaire

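### Fructosamine and fasting free fatty acids are assigned to visit windows with no row for several of their scheduled weeks, so those samples are reported under the wrong week

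*SAP*

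**What the plan says.** SAP 4.8.2 sets the default for laboratory parameters, with efficacy parameters set aside: "blood samples for clinical laboratories will be collected at the protocol scheduled visits, and visits will be assigned to the Global Analysis Windows". Under its Other group the same section lists "Fasting Leptin, Pregnancy test (serum/urine), Fasting Free Fatty Acids, Hepatitis B surface antigen (sAg), HIV (Ab), HbA1c, Fasting Apolipoprotein C3, Fructosamine", with no exception for fructosamine or FFA. SAP 4.7 does not count either analyte as efficacy: "Efficacy will be assessed through the following parameters: fasting TG, HbA1c, fasting glucose, liver fat content as measured by MRI-PDFF, and lipodystrophy hunger questionnaire outcomes".

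The Global windows are SAP Table 8. No other window table visible in Appendix 10.2 names fructosamine or FFA. Body weight (Table 10), fasting TG and glucose (Table 11) and HbA1c (Table 12) each have their own. Appendix 10.2 says of the windows: "These visit windows reflect the study schedule of assessments as described in the protocol". SAP 6.4 adds that when several values fall in one window, the one nearest the target day is used, with ties going to the later value.

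**The concern.** Table 8 is built on the hematology and chemistry schedule, while fructosamine and FFA are drawn on a different one. A by-visit table produced as written would have no row for several weeks at which these samples are taken. It would show values under weeks at which they are not scheduled, and in some cases would combine two visits in one row and discard a valid sample. This departs from the SAP's own statement that the windows reflect the protocol schedule.

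At stake is the readability of the descriptive summaries of these two analytes over the first weeks of each treatment period: the laboratory tables of SAP 5.8.4 and the by-visit biomarker statistics promised in Protocol 11.4.8. The plan had 10 patients per arm and cohort, and SAP 1.2.4 records that the study ended early with fewer patients than planned, so a discarded or misplaced value is more visible than in a large trial.

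**Working it through.** **Inputs.** The schedule of events (Protocol Table 2, SAP Table 22) gives these weeks to week 24, with visits allowed ±3 days:

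- Hematology and chemistry: 1, 3, 6, 8, 10, 12, 13, 15, 17, 18, 20, 22, 24. These are exactly the Table 8 labels.
- Fructosamine: 2, 4, 6, 8, 10, 12, 14, 16, 18, 20, 22, 24.
- FFA: 2, 4, 6, 10, 12, 16, 18, 22, 24 (no week 8, 14 or 20).

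Table 8 windows, with single-blind (SB) days counted from the first single-blind dose: Week 1 = days 2–15; Week 3 = days 16–32 (target 22); Week 13 = SB 2–15; Week 15 = SB 16–29 (target 22); Week 17 = SB 30–39; Week 18 = SB 40–50.

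**Step 1: labels.** SB day 1 is taken as day 85.

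| Scheduled draw | Nominal day | Label on nominal day | Labels over ±3 days |
|---|---|---|---|
| Week 2 (both) | 15 | Week 1 | days 12–15 Week 1; 16–18 Week 3 |
| Week 4 (both) | 29 | Week 3 | days 26–32 all Week 3 |
| Week 14 (fructosamine) | SB 15 | Week 13 | SB 12–15 Week 13; 16–18 Week 15 |
| Week 16 (both) | SB 29 | Week 15 | SB 26–29 Week 15; 30–32 Week 17 |

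No allowed day gives any of these draws its own week. Weeks 6–12 and 18–24 are labelled correctly.

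**Step 2: competition for Week 3.** There are 7 × 7 = 49 combinations of week-2 and week-4 days. The two share Week 3 when week 2 is drawn on days 16, 17 or 18: 3 × 7 = 21. Distances to target day 22 are 6, 5 and 4 for those week-2 days, and 4 to 10 for week-4 days 26–32. With ties going to the later value:

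- Day 16: the week-4 draw is kept when its distance is 4, 5 or 6 (3 cases), otherwise week 2 (4 cases).
- Day 17: 2 and 5.
- Day 18: 1 and 6.

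So week 2 is dropped in 3 + 2 + 1 = 6 combinations and week 4 in 4 + 5 + 6 = 15. On nominal days nothing is dropped.

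**Step 3: competition for Week 15 (fructosamine only).** With the first single-blind dose on day 85, both draws fall in Week 15 when week 14 is on SB 16–18 and week 16 on SB 26–29: 3 × 4 = 12 of 49. Each sample is dropped in 6.

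The day-85 visit itself has ±3 days. If that dose shifts by d days, week 14 reaches Week 15 on 3 − d of 7 days, and week 16 stays in Week 15 on d + 4 of 7 days. Summing (3 − d)(d + 4) over d = −3 to 3 gives 6 + 10 + 12 + 12 + 10 + 6 + 0 = 56 of 343, or 16%.

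**Step 4: does week 18 stay clean if the day-85 dose moves?** Not entirely. Its SB day is 43 + e − d, where e is the draw's own shift. It falls to 39 or below, and so into Week 17, when e ≤ d − 4: 1 + 2 + 3 = 6 of 49 combinations. Week 16 is in Week 17 at the same time in 2 × 1 + 1 × 2 = 4 of 343. Weeks 20, 22 and 24 stay in their own Table 8 windows.

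**Step 5: Table 11 boundaries.** Week 2 = days 2–22, Week 4 = 23–36, Week 14 = SB 2–22, Week 16 = SB 23–36. Every allowed day for these four draws gets its own label, with 0 of 49 collisions in each period. This holds when the day-85 dose moves too, since the SB ranges become 9–21 and 23–35.

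**The case against.** The strongest counter-argument is that the text is incomplete. The exploratory endpoints in Protocol 4.3 are blank, and SAP 4.9 breaks off part-way. Insulin, drawn at the same weeks as FFA, appears neither in the SAP 4.8.2 list nor in any visible window table, which suggests that some metabolic analyses sit in removed text. SAP 5.9 refers to the Analysis Windows without naming the Global ones. The Other list in 4.8.2 also contains HbA1c, which has Table 12, so being listed does not by itself prove that Table 8 governs. This stands as a reason for moderate confidence. It does not remove the problem: the visible rule points to Table 8, and if these analytes were exempt from it they would have no visible named window.

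Three stronger readings are tempting and are not supported.

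- A reader might infer that both analytes are affected at all four weeks. FFA has no week-14 draw, so it cannot compete for Week 15.
- A reader might turn 21 of 49 into a statement that 43% of patients lose an early sample. That needs visit days spread evenly over ±3 days, which no document states. A sample that is not selected is also missing only from its by-visit row; under SAP 5.8 the abnormal-value counts use all evaluations.
- A reader might infer that the evidence for early response is damaged. The Protocol 3.2.1 rationale for treatment duration cites glucose, TG, HbA1c and liver fat, which have their own windows in Tables 11, 12 and 14. It does not cite fructosamine or FFA.

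**Conclusion.** The point holds as a limited defect in the SAP. On the visible text, fructosamine draws at weeks 2, 4, 14 and 16 and FFA draws at weeks 2, 4 and 16 always receive the wrong week label, even with perfect attendance. That part needs no assumption about visit timing.

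Loss of a sample is conditional. In the double-blind period it requires a week-2 draw one to three days late. In the single-blind period it depends on where draws fall relative to the first single-blind dose. The counts (21 of 49; 12 of 49, or 56 of 343) weight every allowed day equally and show what the rule can do, not how often it will.

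The consequence is limited to descriptive by-visit laboratory and biomarker summaries. Primary and secondary endpoints are unaffected. Labels for weeks 6–12 and 20–24 are right for draws within the visit window; week 18 is also right unless the day-85 dose is late and the week-18 draw early. Priority is low and confidence moderate because of the redaction.

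**What to change.** In SAP 4.8.2 and Appendix 10.2, name the windows for fructosamine, fasting FFA and any index built on FFA, so that the components of an index come from the same visit. Table 11 gives the right boundaries for weeks 2, 4, 14 and 16.

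A dedicated table is slightly cleaner than using Table 11 whole. Table 11 has a Week 23 row (SB 75–81) at which neither analyte is drawn. If the day-85 dose moves, a week-22 draw (SB 71 ± 6) or a week-24 draw (SB 85 ± 6) can land there, in 6 of 49 combinations each. Taking weeks 2, 4, 6, 14, 16 and 18 from Table 11 and weeks 8, 10, 12, 20, 22 and 24 from Table 8 avoids this: the boundaries join at days 50/51 in both periods, and every allowed draw keeps its own label.

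Report only the weeks at which each analyte is scheduled, so FFA would have no week 8, 14 or 20 row. The cost is a short SAP edit and a programming lookup; no data collection changes. If removed text in SAP 4.9 already sets such a rule, a cross-reference from 4.8.2 is enough.

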#### Hematology:

- Red blood cells and platelets: hemoglobin, hematocrit, erythrocytes count, platelets count, red blood indices
- White blood cells: white blood cells, neutrophils, lymphocytes, monocytes, basophils, eosinophils

#### Clinical chemistry:

- Electrolytes: sodium, potassium, chloride, carbon dioxide, calcium
- Metabolism: fasting glucose, total protein, albumin, Creatine phosphokinase
- Renal function: creatinine, blood urea nitrogen (BUN), uric acid
- Liver function: Alanine aminotransferase (ALT), aspartate aminotransferases (AST), alkaline phosphatase (ALP), total bilirubin, LDH, Gamma-glutamyl transferase (GGT)

#### Fasting Lipid Panel

• HDL-C, LDL-C, TC, Apo B, TG, NMR lipoprotein analysis

#### Urinalysis

• Color, clarity, pH, specific gravity, ketones, protein, glucose, blood, bilirubin, leukocyte esterase, nitrite, WBC, RBC

## Regeneron Pharmaceuticals, Inc.

Page 27 of 88

Protocol: R4461-PLD-20100

## Other

• Fasting Leptin, Pregnancy test (serum/urine), Fasting Free Fatty Acids, Hepatitis B surface antigen (sAg), HIV (Ab), HbA1c, Fasting Apolipoprotein C3, Fructosamine, Hepatitis C (Ab), Fasting ANGPTL3, Urine albumin and creatinine

Protocol: R4461-PLD-20100

Date: May 16, 2024

# 4.8.3. Vital Signs

Vital signs parameters will include weight (kg), height (cm), BMI (kg/m²), respiratory rate (breaths/min), temperature (C), systolic and diastolic blood pressures (mmHg), and pulse (bpm) after the patient has been sitting or in the supine position. Both actual values and "change from baseline" values (defined as the post-baseline value minus the baseline value) will be used in the result summaries, and visits will be assigned to the Global Analysis windows (see Appendix 10.2). Potentially clinically significant values (PCSV) ranges will be applied to the vital sign parameter values as applicable (see Appendix 10.4 for PCSV definitions).

# 4.8.4. 12-Lead Electrocardiography (ECG)

A standard 12-lead ECG will be performed at specified time points according to Appendix 10.7. Heart rate will be recorded from the ventricular rate and the PR, QRS, and QT and QTcF intervals will be recorded. Electrocardiogram assessments will be described as normal or abnormal, and visits will be assigned to the Global Analysis Windows (see Appendix 10.2). Potentially clinically significant values (PCSV) ranges will be applied to the selected ECG parameter values as applicable (see Appendix 10.4 for PCSV definitions).

## 4.8.5. Physical Examination Variables

Physical examination will be conducted at the protocol scheduled visits (See Appendix 10.7 for schedule of event). The result is an outcome of normal, abnormal, and if abnormal then clinically significant (Yes/No, not examined), and visits will be assigned to the Global Analysis Windows (see Appendix 10.2).

## 4.9. Other Variables

Other assessment endpoints are listed and defined below. Protocol schedule visits will be assigned to Analysis Windows (See Appendix 10.2).

- Change from baseline in body composition (including absolute and percent lean mass and fat mass) using DXA at weeks 12 and 24 (only at sites with whole body DXA capability). DXA analysis will occur on variables included but not limited to those listed in Appendix 10.6.
- Change from baseline

Regeneron Pharmaceuticals, Inc.

Page 28 of 88

#### 4.10. Pharmacokinetic Variables

Pharmacokinetic (PK) variables include concentrations of total drug and time as specified in the protocol.

# 4.11. Immunogenicity Variables

The immunogenicity variables include anti-drug antibody (ADA) status, and titer at nominal sampling time/visit. Serum samples for ADA will be collected at the clinic visits specified in Appendix 10.7.

#### 4.12. Clinical Outcomes Assessment

# **4.12.1.** Hunger

# **Daily Lipodystrophy Hunger Questionnaire**

The daily lipodystrophy hunger questionnaire was developed to assess hunger related behaviors among patients with lipodystrophy. Patients will complete the PRO assessments daily. The Hunger questionnaire is self-administered and contains 4 items: highest level of hunger, lowest level of hunger, how much time felt hungry, and frequency of fullness after eating meals or snacks. Each item is furnished with 5 response categories; and a numerical value is assigned to each response category as follows:

	Value Assigned to Each Category				
Item	0	1	2	3	4
1. How would you rate your highest level of hunger you felt today?	Not hungry at all	A little hungry	Moderately hungry	Quite hungry	Extremely hungry
2. How would you rate the lowest level of hunger you felt today?	Not hungry at all	A_little hungry	Moderately hungry	Quite hungry	Extremely hungry
3. How much time did you feel hungry today?	None of the time	A little of time	Some of the time	Most of the time	All of the time
4. How often did you feel full after eating meals or snacks today?	Every time	Most of the time	Some of the time	A little of the time	None of the time

## **Patient Global Impression of Severity-Hunger**

The Patient Global Impression of Severity (PGI-S) – Hunger is an anchor-based assessment used to interpret meaningful change of the Hunger PRO. PGI-S–Hunger endpoints consists of the number and percentage of responses for each category at baseline and weeks 12 and 24 as well as categorical shift responses from baseline to week 12 and 24.

Protocol: R4461-PLD-20100

